## LIST OF ABBREVIATIONS

IMPD	Investigational Medicinal Product Dossier
INR	International Normalized Ratio
i.v.	Intravenous(ly)
IRB	Institutional Review Board
LDH	Lactate dehydrogenase
LUMC	Leiden University Medical Center
Max	Maximum
MedDRA	Medical Dictionary for Regulatory Activities
Min	Minimum
NONMEM	Nonlinear Mixed Effects Modeling
PD	Pharmacodynamic
PK	Pharmacokinetic
RIVM	Dutch Centre for Infectious Disease Control
SAE	Serious Adverse Event
SAP	Statistical Analysis Plan
SARS- COV-2	Coronavirus
SD	Standard Deviation
SEM	Standard Error of the Mean
SOC	System Organ Class
SOP	Standard Operating Procedure
SPC	Summary of Product Characteristics
SUSAR	Suspected Unexpected Serious Adverse Reaction
t.i.d.	ter in diem / three times a day
t 1/2	Terminal Elimination Half-life
t lag	Absorption lag time
t max	Time to attain C max
ULN	Upper Limit of Normal
V z /F	Apparent volume of distribution during the terminal elimination phase after extravascular administration
WHO	World Health Organization
WBP	Personal Data Protection Act; in Dutch: Wet Bescherming Persoonsgevens
WMO	Medical Research Involving Human Subjects Act; in Dutch: Wet Medisch- wetenschappelijk Onderzoek met Mensen.

## **PROTOCOL SYNOPSIS**

#### Title

Randomized, double-blind, placebo-controlled, two way crossover, single centre study evaluating the acute and chronic effect of clonazepam on cognitive tests and patient-reported outcome measures in patients with ARID1B-related intellectual disability.

#### Short Title

Clonazepam in ARID1B Evaluation (CARE study)

#### **Background & Rationale**

Intellectual disability (ID) is one of the most frequent neurodevelopmental disorders and affects up to 2-3% of the population [1, 2]. Heterozygous truncating mutations in ARID1B, leading to haplo-insufficiency, are found to be the most frequent cause of ID, explaining about 1% of the patients [3, 4]. Besides non-specific ID, ARID1B mutations have been identified in a high proportion (>50%) of patients with a clinical diagnosis of Coffin-Siris syndrome [5-7]. This syndrome was first described in 1970 as a combination of facial features, hypertrichosis, and fifth digit nail hypoplasia. Other symptoms that have been reported are epilepsy, feeding disorders, congenital heart disease, speech impairment and agenesis of the corpus callosum [8, 9]. Although there are no good estimates of incidence and prevalence, ~50 patients with ARID1B mutations are currently known in the LUMC's expertise center. Worldwide the largest group of described patients consists of 143 [8]. Except for supporting therapies such as physiotherapy and speech therapy, no treatment options are available for ARID1B patients.

In the past two years three Arid1b-haploinsufficient (Arid1b+/-) mice models have been generated and investigated. Arid1b+/- mice display increased anxiety, reduced memory, learning and social interaction [10-13]. A study with mouse brain tissue revealed that the amount of GABAergic inhibitory interneurons, was reduced [11]. This prompted investigation of the ratio of inhibitory and excitatory synapses, which indeed showed a reduction of GABAergic inhibitory synapses [11]. Further analysis showed increased apoptosis in the progenitor population in the medial ganglionic eminence, which is the likely cause of the reduced numbers of inhibitory interneurons since it is the origin of 60-80% of cortical interneurons. Subsequently investigators decided to administer a single treatment of 0.0625 mg/kg i.p. clonazepam in adult Arid1b+/- mice, leading to restored recognition and social memory, and reduced anxiety-like behavior, but not depression-like behavior symptoms 30-60 min after treatment [11]. To provide further support for the involvement of the GABAergic system, the LUMC department of Clinical Genetics, generated ARID1B haploinsufficient (ARID1B+/-) and ARID1B knockout (ARID1B-/-) induced pluripotent stem cells and noticed that the GABAergic interneurons cell number sharply decreased with decreasing functioning copies of ARID1B (unpublished data). This all has led to the hypothesis that haploinsufficiency of ARID1B leads to fewer interneuron progenitors and GABAergic inhibitory interneurons, and an imbalance in excitatory/inhibitory synapses, whilst providing stimulation to the GABAergic system restores this balance and at least partially restores the consequences on behavior and cognition.

Clonazepam (Rivotril) is a nonselective benzodiazepine with a half-life of 20-40 hours, and a tmax of 1–4 hours after oral dosing, and is currently used for treatment of seizures in children and adults

and occasionally for behavioral problems. Recently an exploratory study (CHDR1828) was conducted to investigate the neurocognitive phenotype in 12 ARID1B patients aged 2-31 years and 12 age-matched controls. Based on previous experience and literature we selected a subset of tests of the NeuroCart® (CHDR1828). Important results of these study were that tests for animal fluency, eye movements (saccadic peak velocity and smooth pursuit), body sway, finger tapping and adaptive tracking could be performed adequately by ARID1B patients. Most of these biomarkers have previously been evaluated in benzodiazepines [14, 15]

Plasma sampling is not desirable in the ARID1B patient population, therefore we will first establish the relations between clonazepam plasma concentrations and saliva in healthy volunteers, **Part A**. Such correlation was previously established for diazepam [16]. The study will continue with **Part B**, a two way crossover study evaluating the effect of clonazepam on cognitive tests in 20 patients with ARID1B syndrome.

#### Study objectives

- To test the hypothesis that clonazepam administration has acute beneficial effects compared to placebo on neurocognitive tests.
- To test the hypothesis that multiple-doses clonazepam has beneficial effects compared to placebo on behaviour and cognitive function in ARID1B patients as measured by the ABC, and CGI-I scale.
- Assess safety and tolerability of clonazepam in ARID1B-patients.
- To explore the feasibility of using saliva PK to predict plasma PK
- To assess the potential of at-home neurocognitive tests for the evaluation of treatment effects in children with neurodevelopmental disorders.
- To assess and compare the difference in predictive capability between linear and nonlinear (NONMEM) regression of the saliva:plasma relationship.

#### Study design

**Part A.** Open label study in 20 healthy volunteers where pharmacokinetics of clonazepam will be measured in paired plasma and saliva samples. Detailed scheduling can be found in **Table 1**.

**Part B.** Two-way cross over, placebo-controlled randomized study in patients with ARID1Brelated intellectual disability. Each period will be 22 days and periods will be separated by a threeweek washout. Patients will be monitored in the clinic for 5 hours for safety, PK, and biomarker effects on day 1 and 22 in both periods. Between those days, patients remain at home and fill in questionnaires and wear digital technologies. Detailed scheduling can be found in **Table 2**.

#### Investigational drug

#### Part A

• Clonazepam (Rivotril) droplets for oral use, solution 2.5 mg/ml, dissolved in lemonade. Dose: 0.5 mg or 1 mg, both administered to 50% of subjects.

## Part B

- Active medication. Clonazepam (Rivotril) droplets for oral use, solution 2.5 mg/ml, dissolved in lemonade, tea or juice.
- Placebo: dissolved in lemonade, tea or juice

Study drug or placebo during part B will be administered to the subjects as follows:

- Day 1-3: Starting dose is 0.005 mg/kg, twice daily (max 0.5 mg, twice daily)
- Day 4-6: 0.01 mg/kg, twice daily (max 0.5 mg, twice daily)
- Day 7-22: 0.015 mg/kg, twice daily (max 0.5 mg, twice daily)

Patients will receive a single starting dose at their first visit of 0.005 mg/kg (max 0.5 mg). Patients will be monitored for 5 hours for safety, PK, and biomarker effect. If the dose on day 1 is well tolerated, patients will take the same dose before bedtime, and continue this regimen as described.

After three days, the (adverse) effects will be evaluated by phone. If the dose on day 1 is well tolerated, the dose will be increased to 0.01 mg/kg/day. After another three days, the effects will be evaluated again, after which the dose will be increased to 0.015 mg/kg/day. During these dosing adjustments, the maximum dose will not exceed 0.5 mg, twice daily. In case of relevant adverse events during any of the dose evaluations, the daily dose will be halved. Then, after three days without relevant adverse events, the dose will be increased to the dose that was prescribed at the time adverse events appeared. When relevant adverse events re-appear, subjects will continue at the lowest tolerable dose.

At the end of the study period, clonazepam will be tapered by decreasing the daily dose by 0.01 mg/kg/day every three days.

#### Subjects / Groups

Part A: healthy volunteers (n = 10-20) will be recruited.

Part B. Patients with ARID1B-related ID (n = 20) will be drawn from the LUMC's expertise centre for Coffin-Siris syndrome which currently has about 60 patients. If required, additional patients will be identified through the 8 clinical genetic laboratories who may have diagnosed ARID1B patients.

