#### Sample Size Justification and statistical methodology

For part A, Linear and non-linear relationships between plasma and saliva concentrations will be explored. In the case of a nonlinear relationship, which could be expected due to delayed penetration in the salivary compartment, it is widely accepted that around 20 subjects are necessary to develop a reliable model. The predictive capability of the two regression equations will be compared to determine which method is superior.

For part B, the sample size is based on practical considerations (the total ARID1B population in the Netherlands) and based on the previous study (CHDR1828). We consider 20 patients to be a feasible amount of subjects to recruit, while obtaining sufficient power to detect clinically relevant treatment effects. To establish treatment effects the repeatedly measured cross-over PD endpoints will be analyzed by mixed model analyses of variance with treatment, period, time, and treatment by time as fixed effects, with subject, subject by treatment and subject by time as random effect, and with the (average) baseline value as covariate. The PK-PD relationship between clonazepam concentration and PD endpoints will be assessed by calculating the estimated plasma concentration using the derived formula in part A of the study.

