## 2 STUDY OBJECTIVES

- To test the hypothesis that clonazepam administration has acute beneficial effects compared to placebo on neurocognitive tests.
- To test the hypothesis that multiple-doses clonazepam has beneficial effects compared to placebo on behaviour and cognitive function in ARID1B patients as measured by the ABC, and CGI-I scale.
- Assess safety and tolerability of clonazepam in ARID1B patients.
- To assess the potential of at-home neurocognitive tests for the evaluation of treatment effects in children with neurodevelopmental disorders.
- To assess and compare the difference in predictive capability between linear and nonlinear (NONMEM) regression of the saliva:plasma relationship.

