## 5.5 Treatment assignment and blinding

#### 5.5.1 Randomization and treatment assignment

Subjects must be randomized in a consecutive order starting with the lowest number.

Subject numbers consist of 3 digits. Subject numbers for part A will consist of 101-120 and subject numbers for part B of 201-220. Stratification for gender takes place in Promasys, by adding key value "F" to subject numbers for females and "M" to subject numbers for males. There will be no reserve subjects. The randomization code will be generated by a study-independent CHDR statistician. The randomization code will be unblinded/broken and made available for data analysis only after study closure, i.e., when the study has been completed, the protocol deviations determined, and the clinical database declared complete, accurate and locked. The randomization code will be kept strictly confidential. Sealed individual randomization codes, per subject and per treatment, will be placed in a sealed envelope containing the labelled 'emergency decoding envelopes' will be kept in a safe cabinet at CHDR.

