#### 9.9 Pharmacokinetic and pharmacodynamic endpoints

#### 9.9.1 Pharmacokinetics

The individual plasma and saliva drug concentrations will be listed by treatment, subject, visit and time. Individual plasma and saliva drug concentrations versus time will be plotted in panel plots for each treatment using both a linear and log y-axis.

The individual plasma and saliva drug concentrations will be summarised (n, mean, SD, %CV, median, Min and Max values) by treatment and time, and will also be presented graphically as mean over time, with standard deviation as error bars.

When an actual sampling time of a drug concentration sample differs from the protocol time by more than 20% and at least 10 minutes the concentration will be excluded from calculation of descriptive statistics and a note will be added to the sample in the listing.

The individual PK parameters (except  $t_{max}$  and  $t_{lag}$ ) will be summarized (n, mean, SD, %CV, geometric mean, geometric %CV, median, Min and Max) and will be presented graphically as boxplots. For  $t_{max}$  and  $t_{lag}$ , the n, median, Min and Max statistics will be reported.

During part A, linear correlations will be assessed between saliva and plasma concentrations of clonazepam. When a linear correlation is found, the resulting formula will be used to estimate plasma concentrations in part B of the study. When there is no linear correlation, a population pharmacokinetic model of plasma and saliva concentrations will be constructed using nonlinear mixed effects modelling via NONMEM. Based on the PK model of plasma clonazepam concentrations in plasma, linear and/or exponential relationships will be explored to predict salivary clonazepam. Exploratory analysis of covariates will be performed on the models concerning the relationships between salivary and plasma clonazepam. The resulting optimal model will then be used to predict plasma concentrations from saliva concentrations in part B of the study.

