### 9.11 Interim analyses

There are no planned interim analyses.

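### Part A is sized at 10-20 in one place and 20 elsewhere, no rule chooses between them, and the nonlinear model said to need about 20 subjects is both required and conditional

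*Protocol*

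**What the plan says.** The protocol gives the size of Part A, directly or by implication, in four places.

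- Synopsis, Subjects / Groups: "Part A: healthy volunteers (n = 10-20) will be recruited".
- Synopsis, Study design: "Open label study in 20 healthy volunteers where pharmacokinetics of clonazepam will be measured in paired plasma and saliva samples".
- Section 5.5.1: "Subject numbers for part A will consist of 101-120".
- Synopsis, Sample Size Justification: if the relationship is nonlinear, "it is widely accepted that around 20 subjects are necessary to develop a reliable model". The same paragraph says nonlinearity could be expected, because penetration into saliva may be delayed.

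Sections 3.1 and 4.1 give no number for Part A, and section 1.4.9 deals only with Part B, so the body of the protocol does not settle the matter. Section 9.11 states: "There are no planned interim analyses".

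On what Part A must deliver, section 2 lists as an objective: "To assess and compare the difference in predictive capability between linear and nonlinear (NONMEM) regression of the saliva:plasma relationship". The synopsis objectives include the same item, and the justification adds: "The predictive capability of the two regression equations will be compared to determine which method is superior". None of these carries a condition. Section 9.9.1 does: "When there is no linear correlation, a population pharmacokinetic model of plasma and saliva concentrations will be constructed using nonlinear mixed effects modelling via NONMEM". If a linear correlation is found, that section takes the linear formula forward to Part B.

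**The concern.** A range for a planned sample size is acceptable when the plan says what determines the final number. Here nothing does. Recruitment could stop at 10 in full compliance with Subjects / Groups, although the only justification offered for Part A says a reliable nonlinear model needs about twice that.

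Part B collects saliva only. The Part A equation or model is therefore the sole route from Part B samples to estimated plasma concentrations, and those concentrations enter the PK/PD analysis in section 9.9.4. Section 1.4.4 describes clonazepam PK as variable. Between-subject variability is what a population model has to capture, and it is learned from the number of subjects more than from the number of samples per subject.

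**Working it through.** **Inputs**
- Size stated in Subjects / Groups: 10 to 20.
- Size stated in Study design: 20.
- Subject numbers in section 5.5.1: 120 − 101 + 1 = 20.
- Size called necessary for the nonlinear model: about 20.
- Dose split in Part A (section 5.1): half the subjects at each of two dose levels.
- Paired sampling times (Table 1, and the nine PK samples in section 7.8): 9 per subject.

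**Can the 20 be reproduced?** No. The protocol gives no precision target, variance, effect size or power for Part A. It rests the figure on what is widely accepted, so no sample size formula applies and the stated figures can only be compared with one another.

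**Comparison**
- Lower bound against stated need: 10 / 20 = 0.50. Upper bound: 20 / 20 = 1.00.
- Subjects per dose level: 10 / 2 = 5 at the lower bound, and 20 / 2 = 10 at the upper.
- Scheduled plasma-saliva pairs: 9 × 10 = 90, and 9 × 20 = 180.

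**Illustration only.** For quantities learned from between-subject differences:
- Ratio of standard errors, n = 10 to n = 20: √(20/10) = 1.41.
- 95% limits for a between-subject SD, as multiples of the estimate and assuming normality, are √((n−1)/χ²) at the 97.5% and 2.5% points of χ² with n − 1 degrees of freedom. For n = 10 they are 0.69 and 1.83. For n = 20 they are 0.76 and 1.46.

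These contrasts hold for any study of 10 versus 20 subjects. They do not measure the prediction error of the Part A equation.

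**Is there a rule that selects a number?** A range would make sense if the first 10 subjects were examined and recruitment stopped once the relation proved linear. Section 9.11 plans no interim analysis, and no other section gives a stopping rule.

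**Is the nonlinear model needed?** Two readings stand side by side. Under section 2, the synopsis objectives and the justification, linear and NONMEM regression are compared in every case, so both must be fitted. Under section 9.9.1, the NONMEM model is built only if no linear correlation is found. If one is found, following section 9.9.1 leaves the objective in section 2 unmet. The two cannot both be followed in that case.

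**The case against.** The strongest defence is that the range is intelligible. The justification ties about 20 subjects to a nonlinear relation, and section 9.9.1 fits NONMEM only when linearity fails. Fewer subjects might then suffice if the relation is linear. This stands as a reading of section 9.9.1. It does not rescue the range, because the objective requires the comparison in either case and nothing in the plan turns an observed linear relation into a decision to stop early.

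It is also fair to say that 20 is evidently the operative plan, and that 10-20 occurs once. The amendment log, used only as background, records that one amendment both removed a Part A interim analysis and added the comparison, so the range may be a leftover. A later entry refers to Part A results already in hand. The document does not say how many subjects took part, so the remedy may now be one of reporting.

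Three stronger readings are tempting, and the documents do not support them.

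- A reader might infer that the comparison itself requires 20 subjects. The justification attaches that figure to developing a reliable nonlinear model. The comparison depends on such a model, but no size is stated for it.
- A reader might infer that the nonlinear model is always needed under the plan. Section 9.9.1 says otherwise, which is why this is a conflict to reconcile.
- A reader might quantify the loss with a confidence interval around the diazepam correlation cited in section 1.4.4. That value belongs to another drug, and an interval with one data pair per subject ignores the nine pairs scheduled for each.

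**Conclusion.** The inconsistency is real in the current text. One statement allows 10-20. Two others fix or imply 20, the justification calls about 20 necessary for a nonlinear model, and no rule selects a number within the range. The unconditional comparison and the conditional NONMEM model also contradict each other.

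The lower bound is 50% of the stated need. Beyond that ratio no shortfall can be computed, because the 20 is a convention without a target behind it. Nothing has been miscalculated. The study is exploratory with no primary endpoint, Part A supports only exploratory PK/PD work, and the treatment comparisons in section 9.9.2 do not depend on it. The point is minor but should be corrected. This conclusion assumes that about 20 is not meant to stretch to 10, and that the objectives in section 2 are meant as written.

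**What to change.** In the synopsis under Subjects / Groups, replace the range 10-20 with 20, to agree with Study design, the justification and the subject numbers in section 5.5.1. With the existing dose split this means 10 subjects per dose level.

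In section 9.9.1, state that both the linear and the NONMEM model will be built, so that the comparison promised in section 2 can be made whatever the shape of the relation.

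If fewer than 20 took part, restate the size justification for the actual number and report the nonlinear model and the comparison as limited by it.

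The cost is small. The first change is wording and adds no subjects to the stated design. The second adds modelling work that the objectives already call for. If the third applies, its price is a more cautious statement about how reliable the model is.

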#### Inclusion criteria

Part A: healthy volunteers

- 1. Healthy male or female volunteers aged 18-30 years.
- 2. Informed consent provided by volunteer.

Part B: ARID1B patients.

- 1. Informed consent provided by both parents, or the legal guardian prior to any study mandated procedure.
- 2. Known mutation in ARID1B.
- 3. Assent provided by the participant.
- 4. Aged 6 years or older.

#### Exclusion criteria

Part A: healthy volunteers

- 1. Disorder that could interfere with saliva production.
- 2. Known hypersensitivity to clonazepam, other benzodiazepines or other excipients of the study medication.
- 3. Treatment with another investigational drug within 3 months prior to screening or more than 4 times a year.
- 4. History or clinical evidence of any disease and/or existence of a surgical or medical condition which might interfere with the absorption, distribution, metabolism or excretion of the study drug.
- 5. History of severe respiratory problems or severe liver- or renal insufficiency.
- 6. Other medical or psychosocial condition or history making the participant unsuitable for participation.
- 7. History or clinical evidence of alcoholism within the 3-year period prior to screening (i.e. regular use of more than 21 units of alcohol/week).

- 8. Clinically significant findings on physical examination.
- 9. Medications with a strong influence on CYP3A4 metabolism.
- 10. Clinically meaningful blood loss (including blood donation), or a transfusion of any blood product within 12 weeks before screening.

Part B: ARID1B patients.

- 1. Clear indication of not wanting to participate during the study.
- 2. Use of benzodiazepines or any other medication or drug with the potential to influence study related endpoints in the investigator's opinion (including e.g. CYP3A4-related drugs).
- 3. Known hypersensitivity to clonazepam, other benzodiazepines or other excipients of the study medication.
- 4. History of severe respiratory problems or severe liver- or renal insufficiency.
- 5. Other medical or psychosocial condition or history making the participant unsuitable for participation as determined by the treating physician or general practitioner.

